2.4. Statistical Analyses

No formal hypothesis will be tested. For each PK endpoint and each treatment comparison described in Section 5.1 Study Treatment Display Descriptors, point estimates and corresponding 90% confidence intervals (CIs) will be constructed for the ratio of the geometric mean of the test treatment to the geometric mean of the reference treatment, $\mu(\text{test})/\mu(\text{reference})$.

3. PLANNED ANALYSES

3.1. Interim Analyses

An interim PK analysis is planned at the end of Part A. PK parameters AUC(0-inf), AUC(0-t), AUC(0-24) and Cmax will be derived using nominal times (see Section 7.1.1.2: Derived Pharmacokinetic Parameters). The formulation to be investigated in Part B will be dependent on the PK profile, relative bioavailability and between-participant variability of the test formulations (DC 475, DC 600 and HPMC 600) compared to the reference formulation (RC). The analysis will be documented in a short report which will be stored in the study Trial Master File, together with the associated analysis outputs and Quality Control documentation.

3.2. Final Analyses

The final planned study population, safety and PK concentration summaries will be performed after the completion of the following sequential steps:

1. All participants have completed the study as defined in the protocol.
2. All required database cleaning activities have been completed and final Source Data Lock (SDL) has been declared by data management (DM).
3. Study is unblinded
 - Randomization schedules are released in RANDALL NG and GSK create and quality control (QC) unblinded RANDALL dataset.
 - SMS2000 data is released in HARP
4. Unblinded RANDALL dataset and SMS2000 file are released to IQVIA by GSK via secure external alliance portal (EAP)
5. Study Data Tabulation Model (SDTM) data conversion has been completed by IQVIA including unblinding activities and QC of unblinded SDTM has been completed by DM.
6. Database freeze (DBF) on unblinded study population, safety and PC SDTM datasets has been declared by DM.

Following this, the PK parameter analyses will be performed after the PP SDTM domain is available.

4. ANALYSIS POPULATIONS

Population	Definition / Criteria	Analyses Evaluated
All Subjects (ALLSUB)	
 • All participants who were screened and for whom a record exist on the study database 	
 • Participant disposition • Reasons for withdrawal prior to randomization • Inclusion/exclusion criteria deviations for non-randomized participants • AEs and SAEs for non-randomized participants
Modified Intent-to-treat (mITT)	
 • All randomized participants apart from those who were randomized in error (i.e. were also recorded as screen failures and did not receive a dose of study treatment). • Any participant who receives a treatment randomization number will be considered to have been randomized. • Randomized participants will be assumed to have received study medication unless definitive evidence to the contrary exists. • If a participant received an incorrect meal or formulation, by-treatment summaries will use the meal/formulation actually received. 	
 • Study population • Safety
Pharmacokinetic (PK)	
 • All participants for whom a pharmacokinetic sample was obtained and analysed 	
 • PK

Refer to [Appendix 10: List of Data Displays](#) which details the population used for each display.

If the PK and mITT populations include the same participants then the PK analysis will be run on the mITT population and data will be excluded as detailed in [Section 7](#)

4.1. Protocol Deviations

Protocol deviations (PDs) will be handled as described in [Appendix 1: Protocol Deviation Management](#). A Per Protocol population will not be defined.

5. CONSIDERATIONS FOR DATA ANALYSES AND DATA HANDLING CONVENTIONS

5.1. Study Treatment Display Descriptors

All participants will receive DNX 50mg in each treatment period. The term 'treatment' refers to the combination of formulation and meal as identified below.

Treatment Group Descriptions			
RandAll NG		Data Displays for Reporting	
Code	Description	Description	Order in TLF
A	DNX 50mg 600RC High fat Formulation 1	DNX 50mg 600RC High fat – A	1
B	DNX 50mg 475DC High fat Formulation 4	DNX 50mg 475DC High fat – B	2
C	DNX 50mg 600DC High fat Formulation 2	DNX 50mg 600DC High fat – C	3
D	DNX 50mg 600DC 5%HPMC High fat Formulation 3	DNX 50mg 600DC 5%HPMC High fat – D	4
AO	DNX 50mg 600RC Fasted Formulation 1	DNX 50mg 600RC Fasted – AO	5
BO	DNX 50mg 475DC Fasted Formulation 4	DNX 50mg 475DC Fasted – BO	6
CO	DNX 50mg 600DC Fasted Formulation 2	DNX 50mg 600DC Fasted – CO	7
DO	DNX 50mg 600DC 5%HPMC Fasted Formulation 3	DNX 50mg 600DC 5%HPMC Fasted – DO	8
E	DNX 50mg Fasted	DNX 50mg Fasted – E	9
F	DNX 50mg Normal meal	DNX 50mg Normal meal – F	10
G	DNX 50mg High fat	DNX 50mg High fat – G	11
H	DNX 50mg MONO High fat	DNX 50mg MONO High fat – H	12
I	DNX 50mg Fasted OMP	DNX 50mg Fasted OMP – I	13
J	DNX 50mg Normal meal OMP	DNX 50mg Normal meal OMP – J	14
K	DNX 50mg High fat OMP	DNX 50mg High fat OMP - K	15

Treatment comparisons will be displayed as follows using the comparison column as specified:

Part	Question	Comparison	Comparison Description
Part A Group 1	Formulation in the fed state	475mg DC tablet formulation versus 600mg RC formulation (reference)	B vs A
		600mg DC tablet formulation versus reference	C vs A
		600mg DC tablet with 5% HPMC versus reference	D vs A
Part A Group 2	Formulation in the fasted state	475mg DC tablet formulation versus 600mg RC formulation (reference)	BO vs AO
		600mg DC tablet formulation versus reference	CO vs AO

Part	Question	Comparison	Comparison Description
		600mg DC tablet with 5% HPMC versus reference	DO vs AO
Part A Group 1 & 2	Food effect	600mg RC formulation fed versus fasted	A vs AO
		475mg DC tablet formulation fed versus fasted	B vs BO
		600mg DC tablet formulation fed versus fasted	C vs CO
		600mg DC tablet with 5% HPMC fed versus fasted	D vs DO
Part B Group 1	Food effect, no OMP	High fat meal (heavy) versus fasted	G vs E
		Normal meal (light) versus fasted	F vs E
		High fat meal (heavy) versus normal meal (light)	G vs F
Part B Group 2	Food effect with OMP	High fat meal (heavy) versus fasted	K vs I
		Normal meal (light) versus fasted	J vs I
		High fat meal (heavy) versus normal meal (light)	K vs J
Part B Group 1 & 2	Drug interaction	Fasted with OMP versus fasted without OMP	I vs E
		Normal meal (light) with OMP versus normal meal (light) without OMP	J vs F
		High fat meal (heavy) with OMP versus high fat meal (heavy) without OMP	K vs G
Part B Group 1	Pharmaceutical development	Monohydrate with high fat meal versus high fat meal (heavy)	H vs G

5.2. Baseline Definitions

Any assessments made after the time of the study treatment dose will not be included in the derivation of baseline. Assessments made on the same day as dosing with a missing time are assumed to be taken prior to first dose.

If baseline data are missing, no derivation will be performed and baseline will be set to missing.

Parameter	Baseline Used in Data Display
ECG values	The average of the triplicate readings made on Day -1 of each treatment period will be calculated and used as period baseline. Any reading made after the time of dosing will not be included in the calculation.
Vital signs (pulse rate, systolic and diastolic blood pressure)	The average of the triplicate readings made pre-dose on Day 1 of each treatment period as recorded on the electronic case report form (eCRF) will be used as period baseline
Laboratory data	The assessment made on Day -1 of the first treatment period will be used as a study baseline

5.3. Multiple Comparisons and Multiplicity

No adjustments for multiplicity will be made.

5.4. Other Considerations for Data Analyses and Data Handling Conventions

Other considerations for data analyses and data handling conventions are outlined in the appendices:

Section	Component
10.3	Appendix 3: Assessment Windows
10.4	Appendix 4: Study Phases
10.5	Appendix 5: Data Display Standards & Handling Conventions
10.6	Appendix 6: Derived and Transformed Data
10.7	Appendix 7: Reporting Standards for Missing Data
10.8	Appendix 8: Values of Potential Clinical Importance

6. STUDY POPULATION ANALYSES

6.1. Overview of Planned Study Population Analyses

Study population analyses including analyses of participant disposition, protocol deviations, demographic and baseline characteristics, relevant medical history and concomitant medications will be based on GlaxoSmithKline (GSK) Core Data Standards. Results will generally be presented for all participants with a Part and Group, not split by treatment. Details of the split for each display are included in Section [10.10.4](#) Study Population Tables.

A summary of the number and percentage of participants who completed each treatment period and entered and completed each washout period, along with the reasons for withdrawal, will be displayed for each Part and Group separately. Separate study treatment compliance and exposure displays will not be produced as they would contain the same information.

Compliance with OMP will be summarized by treatment for treatments I, J and K.

Meal data will be summarized by treatment.

Details of the planned displays including the population to be used for each display are presented in [Appendix 10: List of Data Displays](#).

7. PHARMACOKINETIC ANALYSES

7.1. Primary Pharmacokinetic Parameter Analyses

The primary PK parameter analysis is to compare the relative bioavailability of different formulations of danirixin in the fed and fasted states. The primary treatment effect to be estimated is the ‘as-treated’ effect of treatment (formulation and meal) in participants who consume at least 90% of the meal (in fed participants) and provided an adequate PK concentration profile to allow reliable estimation of PK parameters.

7.1.1. Endpoint / Variables

- Log-transformed AUC(0-inf) and Cmax.

The following secondary endpoints which are analysed in the same way as the primary endpoints and assess the same outcome are also included in this section:

- Log-transformed AUC(0-t), AUC(0-24) and t1/2.

The following parameters will not be log-transformed and will be included in summary tables containing untransformed values for the primary endpoint.

- tmax, tlag, tlast.

7.1.1.1. Drug Concentration Measures

Refer to [Appendix 5: Data Display Standards & Handling Conventions \(Section 10.5.3 Reporting Standards for Pharmacokinetics\)](#)

7.1.1.2. Derived Pharmacokinetic Parameters

Pharmacokinetic parameters will be calculated by standard non-compartmental analysis according to current working practices and using the currently supported version of WinNonlin. All calculations of non-compartmental parameters will be based on actual sampling times. Pharmacokinetic parameters listed will be determined from the blood concentration-time data, as data permits. If parameters cannot be determined, a ‘Not done’ or ‘Not calculable’ flag will be present in the data. In addition, parameters affected by the other intercurrent events identified in Section 7.1 will also be identified in the data.

Parameter	Parameter Description
AUC(0-inf)	Area under the concentration-time curve extrapolated to infinity will be calculated as: $AUC = AUC(0-t) + C(t) / \lambda_z$
Cmax	Maximum observed concentration, determined directly from the concentration-time data.
AUC(0-t)	Area under the concentration-time curve from time zero to the time of the last quantifiable concentration (C(t)) will be calculated using the linear trapezoidal rule for each incremental trapezoid and the log trapezoidal rule for each decremental trapezoid.
AUC(0-24)	Area under the concentration-time curve from time zero to 24 hours will be calculated using the linear trapezoidal rule for each incremental trapezoid and the log trapezoidal rule for each decremental trapezoid.
Tmax	Time to reach Cmax, determined directly from the concentration-time data.
t1/2*	Apparent terminal half-life will be calculated as: $t_{1/2} = \ln 2 / \lambda_z$
Tlag	Lag time before observation of drug concentrations in blood
Tlast	Time of last quantifiable concentration

* associated parameters λ_z , λ_z _lower, λ_z _upper, No_points_ λ_z to be listed.

NOTES:

- Additional parameters may be included as required.
- λ_z is the terminal phase rate constant.

7.1.2. Summary Measure

Relative bioavailability of danirixin after single dose of three formulations of HBr tablet (DC) versus HBr tablet (RC) in fed and fasted states.

- Fed (treatment comparisons B vs A, C vs A, D vs A)
- Fasted (treatment comparisons BO vs AO, CO vs AO, DO vs AO)

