**Rationale:**

Part A of this study will provide an understanding of the PK of 3 test tablet formulations of the HBr salt of danirixin in healthy elderly participants in fed and fasted conditions in comparison to the current HBr salt tablet formulation. The current formulation is a hemihydrate salt tablet formulation manufactured using roller compaction (RC). The test formulations are manufactured by direct compression (DC) and will investigate the performance of these DC tablets, as well as the inclusion of the excipient hydroxypropyl methylcellulose (HPMC). Formulation selection for Part B will occur following review of the PK data collected in Part A.

Part B of this study will provide an understanding of the PK using the selected formulation from Part A in the fed and fasted state; during gastric acid suppression and in the monohydrate state under fed conditions in a population of healthy elderly participants. Danirixin is currently administered with food, therefore the investigation of food effect for the selected formulation could potentially enable dosing without food. Additionally, omeprazole (OMP) is being administered with the selected formulation to investigate a potential PK interaction as gastric pH has been shown to alter PK exposure and this study will further enable us to investigate OMPs influence in the presence and absence of food. Finally, the monohydrate tablet simulates a hemihydrate to monohydrate tablet in stressed conditions.

The outcome of this study will contribute to the selection of the most appropriate formulation/dosing regimen for future studies.

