**Table 4 Part A Treatment Descriptions**

Treatment Arm	Description	Danirixin Dosing Regimen (or Frequency)
A	1 x 50 mg danirixin HBr tablet (600 mg RC formulation) reference formulation; fed state high fat meal (heavy)	single dose
B	1 x 50 mg danirixin HBr tablet (475mg DC formulation); fed state high fat meal (heavy)	single dose
C	1 x 50 mg danirixin HBr tablet (600 mg DC formulation); fed state high fat meal (heavy)	single dose
D	1 x 50 mg danirixin HBr tablet (600 mg DC tablet formulation with 5% HPMC); fed state high fat meal (heavy)	single dose
AO	1 x 50 mg danirixin HBr tablet (600 mg RC formulation) reference formulation; fasted	single dose
BO	1 x 50 mg danirixin HBr tablet (475mg DC formulation); fasted	single dose
CO	1 x 50 mg danirixin HBr tablet (600 mg DC formulation); fasted	single dose
DO	1 x 50 mg danirixin HBr tablet (600 mg DC tablet formulation with 5% HPMC); fasted	single dose

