# **10. STATISTICAL CONSIDERATIONS**

No formal hypothesis will be tested. For each pharmacokinetic endpoint, point estimates and corresponding 90% confidence intervals will be constructed for the ratio of the geometric mean of the test treatment to the geometric mean of the reference treatment,  $\mu(\text{test})/\mu(\text{reference})$ .

The following comparisons of interest will be constructed:

Part	Question	Comparison
Part A Group 1	Formulation fed	475mg DC tablet formulation versus 600mg RC formulation (reference)
		600mg DC tablet formulation versus reference
		600mg DC tablet with 5% HPMC versus reference
Part A Group 2	Formulation fasted	475mg DC tablet formulation versus 600mg RC formulation (reference)
		600mg DC tablet formulation versus reference
		600mg DC tablet with 5% HPMC versus reference
Part A Group 1 & 2	Food effect	600mg RC formulation fed versus fasted
		475mg DC tablet formulation fed versus fasted
		600mg DC tablet formulation fed versus fasted
		600mg DC tablet with 5% HPMC fed versus fasted
Part B Group 1	Food effect No OMP	High fat meal (heavy) versus Fasted
		Normal meal (light) versus Fasted
		High fat meal (heavy) versus Normal meal (light)
Part B Group 2	Food effect With OMP	High fat meal (heavy) versus Fasted
		Normal meal (light) versus Fasted
		High fat meal (heavy) versus Normal meal (light)
Part B Group 1 & 2	Drug interaction	Fasted with OMP versus Fasted without OMP
		Normal meal (light) with OMP versus Normal meal (light) without OMP
		High fat meal (heavy) with OMP versus High fat meal (heavy) without OMP
Part B Group 1	Pharm Dev	Monohydrate with high fat meal versus High fat meal (heavy)

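### Part A sets out to look at adding HPMC, but no planned contrast compares the two 600 mg direct-compression tablets without and with HPMC

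*SAP*

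**What the plan says.** The protocol's rationale (Synopsis, repeated in section 3.1) describes Part A as a comparison of three direct-compression (DC) test tablets with the current RC tablet. It adds that the test formulations "will investigate the performance of these DC tablets, as well as the inclusion of the excipient hydroxypropyl methylcellulose (HPMC".

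Table 4 of the protocol describes the three tablets that matter here, in the fed state:

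- A: "1 x 50 mg danirixin HBr tablet (600 mg RC formulation) reference formulation; fed state high fat meal (heavy"
- C: "1 x 50 mg danirixin HBr tablet (600 mg DC formulation); fed state high fat meal (heavy"
- D: "1 x 50 mg danirixin HBr tablet (600 mg DC tablet formulation with 5% HPMC); fed state high fat meal (heavy"

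AO, CO and DO are the same tablets taken fasted.

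For the HPMC tablet, the formulation comparison in Protocol section 10 is "600mg DC tablet with 5% HPMC versus reference", once fed and once fasted. SAP 7.1.2 lists the primary contrasts as "Fed (treatment comparisons B vs A, C vs A, D vs A" and "Fasted (treatment comparisons BO vs AO, CO vs AO, DO vs AO". SAP 5.1 has the same list, and SAP 2.4 ties the 90% intervals to the comparisons in SAP 5.1. The other Part A contrasts (SAP 7.2.2) are fed against fasted within one formulation.

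The formal Part A objective (Protocol section 4, SAP 2.2) is the test formulations against the RC reference.

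**The concern.** D vs A changes two things at once: the process, from RC to DC, and the excipient, from no HPMC to 5%. If the process change moved exposure one way and HPMC moved it back, D/A would sit near 1 and hide both effects. If D/A were far from 1, it would not show which change was responsible. The same holds for DO vs AO.

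The pair closest to the HPMC question is C and D, and the crossover already supplies it within participant. Leaving it off the list means that anything the interim or final report says about HPMC must rest on D vs A, or on judging two intervals against a shared reference by eye. Two later steps touch on this. One is the choice of tablet for Part B, where C and D are both candidates. The other is the HPMC content of the monohydrate tablet, which the treatment table in Protocol 7.1 leaves to be confirmed after Part A.

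**Working it through.** **Which contrasts are planned.** Protocol section 10, SAP 5.1 and SAP 7.1.2 list B, C and D against A, and BO, CO and DO against AO. SAP 7.2.2 adds A vs AO, B vs BO, C vs CO and D vs DO. Tables 2.4 to 2.6 and Figures 2.12 to 2.14 follow these lists. D vs C and DO vs CO appear in none of them.

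**What D vs A estimates.** On the log scale, log(D/A) = log(C/A) + log(D/C). By the Table 4 descriptions, the first term is the change of process and the second is the addition of HPMC. Only the second bears on HPMC.

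**The plan's own precision figure.** Inputs from Protocol 10.1: within-subject CV for Cmax 44.7%, 6 completers per group, stated 90% CI 0.70 to 1.42 at an observed ratio of 1.

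- sd_w = sqrt(ln(1 + 0.447²)) = 0.4268.
- exp(± t(0.95, 5 df) × 0.4268 / sqrt(6)) = 0.704 to 1.421, which reproduces the stated figure.

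That form omits the factor sqrt(2) for a difference between two treatments within a participant. A normal quantile with 8 per group and the factor included gives the same limits, but 8 is the number randomized. This is a separate matter. It is noted only because the intervals below include the factor and so are wider than the protocol's.

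**Precision of D vs C from the planned model.** The SAP's four sequences per group (SAP 2.3) were put into a model with participant, period and eight treatments. With complete data, within-group contrasts use within-participant information only, so treating participant as fixed or random makes no difference to them.

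- 8 per group, complete: SE = 0.4268 × sqrt(2/8) = 0.2134 for both D/C and D/A. Residual df = 64 − 16 − 3 − 6 = 39. 90% CI 0.698 to 1.433.
- 6 per group, losing one participant from each of two sequences, with the same pattern in both groups: residual df = 48 − 12 − 3 − 6 = 27. Across the five patterns tried:

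| Contrast | SE (log scale) | 90% CI at ratio 1 |
|---|---|---|
| D vs C, DO vs CO | 0.248 to 0.250 | lower 0.653 to 0.655, upper 1.526 to 1.532 |
| D vs A | 0.246 to 0.250 | lower 0.653 to 0.657, upper 1.522 to 1.531 |

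For AUC(0-inf), CV 37.3% gives sd_w = 0.3609. Using the simple form with 27 df, exp(± t × 0.3609 × sqrt(2/6)) is about 0.70 to 1.43.

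The missing contrast would therefore be about as precise as the planned ones.

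**The case against.** The planned contrasts match the formal objective exactly. HPMC appears as an aim only in the rationale, in a paragraph that opens by setting the test tablets against the current one. The interim selection (SAP 2.3 and 3.1) is also defined against RC: PK profile, relative bioavailability and between-participant variability compared with the reference. Choosing a tablet on that basis does not require attributing its behaviour to an excipient. The study is estimation-only, with a sample size set mainly by feasibility. All of this stands, and it keeps the point modest.

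A reader might infer that the HPMC effect cannot be recovered at all, because the D/A and C/A intervals share the same A data. The documents do not support that. SAP 7.1.5.1 reports geometric least squares means for each treatment, which give the D/C ratio, and uses one pooled residual variance. In this balanced design the log half-width for D/A can be borrowed: it is exact with complete data and close with the planned dropout. Figure 2.5 and Listings 13 and 35 also show C and D data. What remains is that the shortcut becomes less exact once single periods are excluded under SAP 7.1.4, and that it would be an unplanned calculation.

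A reader might also combine D/A and C/A as if they were independent. The simple SE is 0.4268 × sqrt(2/6) = 0.2464, so this gives exp(± t(0.95, 27 df) × 0.2464 × sqrt(2)), about 0.55 to 1.81. The plan prescribes no such calculation, so that width does not measure the plan's shortfall.

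Finally, Table 4 gives process, tablet size, dose and HPMC but not full composition. If both tablets weigh 600 mg, adding 5% HPMC displaces something else. D vs C is the closest comparison for HPMC, not a proven isolation of it.

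**Conclusion.** The point holds as a gap in pre-specification. Part A's rationale names the inclusion of HPMC, the closest pair for that question is taken by every participant who completes a group, and no interval for that pair is planned. D vs A and DO vs AO should not be read as HPMC effects.

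It would go too far to say that Part A misses its objective or that an HPMC effect drives the choice of formulation. The objective and the selection basis are both stated against RC. The entry for the monohydrate tablet in Protocol 7.1 may mean only that it follows the selected formulation.

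The expected 90% CI for Cmax is about 0.65 to 1.53 around a ratio of 1, similar to D vs A. This assumes the protocol's CV of 44.7%, 6 completers per group with complete periods, and both groups in one model. An interval that wide would say little about a small HPMC effect, and printing it would make that limit plain.

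**What to change.** Add D vs C (fed) and DO vs CO (fasted), as geometric least squares mean ratios with 90% CIs for AUC(0-inf) and Cmax, to:

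- the comparison tables in Protocol section 10 and SAP 5.1, and the list in SAP 7.1.2;
- Tables 2.4 and 2.5 and Figures 2.12 and 2.13;
- the Part A interim report described in SAP 3.1.

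State that any conclusion about HPMC rests on these contrasts and not on D vs A or DO vs AO. While editing, align the treatment table in Protocol 7.1 with Table 4: its HPMC entry for the DC tablets refers to the 600 mg size without separating C from D.

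The cost is two contrast statements in the model already specified and two rows in the displays. No data or participants are added. SAP 5.3 makes no multiplicity adjustment, so the existing intervals do not change.
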